## 6.2. Tafamidis

## 6.2.1. Mechanism of Action

Tafamidis is a selective stabilizer of tetrameric wild-type TTR and of amyloidogenic variants of TTR, of which Val30Met mutation (primarily affecting the peripheral nerves) and Val122Ile mutation (primarily affecting myocardium) are the most abundant. Mixed phenotypic presentations (ie, polyneuropathy and cardiomyopathy) are frequent in non-Val30Met TTR mutations. The underlying mechanism of TTR amyloid disease, regardless of the phenotypic presentation is believed to be an accelerated deposition of the unstable TTR monomers.

Tafamidis binds to the native tetrameric forms of TTR and thereby inhibits tetramer dissociation, the rate limiting step in the formation of TTR amyloid. Tafamidis has an approximate 55-hour half-life and has been demonstrated to achieve stabilization of the TTR tetramer in over 40 mutations and wild-type TTR, for which it was tested. This novel class of TTR stabilizing drug disrupts the progression of ATTR.

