## 6.2.2. Relevant Nonclinical Findings

There was no evidence of adverse effects of tafamidis on fertility, or reproductive performance, or mating behavior in rats. In animal reproductive studies, oral administration of tafamidis meglumine to pregnant rabbits during organogenesis resulted in adverse effects on development (embryofetal mortality, fetal body weight reduction and fetal malformation) at a dose providing approximately 9 times the human exposure area under the curve (AUC) at the maximum recommended human dose (MRHD), and increased incidence of fetal skeletal variations at a dose providing equivalent human exposure (AUC) at the MRHD. Postnatal mortality, delayed male sexual maturation, and impaired learning and memory were observed in offspring of pregnant rats administered tafamidis meglumine during gestation and lactation at a dose approximately 2 times the MRHD based on body surface area (mg/m^2).

Nonclinical studies with tafamidis indicate that there are no effects on the male germ cell before conception. In toxicology studies there was no evidence of genotoxicity, no histopathological changes in testis or epididymis and no effects on male fertility at doses up to 30 mg/kg. Therefore, the risk for male-mediated developmental toxicity is considered to be low because the levels of tafamidis estimated to be transferred in semen are significantly lower than the concentrations that cause developmental toxicity in nonclinical studies.

In summary, anomalies have been observed in rabbit and rat reproductive toxicology studies. In humans, ATTR could present during the patient's reproductive years, although based on our current understanding of age of onset of disease, this is more likely for a patient with ATTR-PN rather than ATTR-CM. On account of the low prevalence of ATTR-PN and ATTR-CM (rare diseases), limited reproductive data are available in humans. There has been a low incidence of exposures reported in women with ATTR-PN in the ongoing TESPO surveillance program from clinical and NI studies over a 7-year period. Nonetheless, given that tafamidis meglumine/tafamidis may cause fetal harm, product labeling recommends avoidance of pregnancy in female patients receiving tafamidis; breastfeeding is also not recommended during treatment with tafamidis. B3461091 will collect and summarize data on pregnancy outcome and birth outcome in women with ATTR exposed to tafamidis during or within 1 month prior to pregnancy.

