## 8. RESEARCH METHODS

## 8.1. Study Design

This is a global, prospective, non-interventional study designed to collect information on pregnancy outcomes in women with ATTR exposed to tafamidis during or who became pregnant within 1 month after discontinuation of drug.

[figure not shown]
This PMR study (B3461091), which is anticipated to start in 2020 and complete in 2030 will utilize routine pharmacovigilance activities in addition to the data collection and process implemented via the ongoing Tafamdis Enhanced Surveillance for Pregnancy Outcomes (TESPO) program, which will be maintained at least until 2030. Time of enrollment is the time of initial awareness of the pregnancy reported by an investigator (clinical trial) or the HCP or patient (non-clinical source). Once initiated, all prospective pregnancy events captured via Study B3461091 (including new data collected in TESPO) will be reported to regulatory agencies in aggregate reports via Study B3461091.

TESPO is descriptive, non-interventional, observational program which has been ongoing since 2011 as an EMA post marketing requirement to assess outcome of pregnancy and birth outcomes (including major birth defects and/or developmental abnormalities in live born children up to 12 months) in female patients with ATTR-PN with exposure to tafamidis during or within 1 month prior to the pregnancy. All TESPO data are collected through use of the standard pharmacovigilance EDP form and follow-up form and the Tafamidis Enhanced Surveillance data capture aid (DCA) and 12-month follow up forms. Collection of data will be updated to include ATTR-CM. Updates will also include maternal assessment at mid-point during pregnancy and 6 month assessment of infant in addition to timepoints already collected. This collection will be achieved by adding a non-standard data collection time point (triggered at 2nd trimester of gestation) and at 6 months post delivery using the standard EDP Follow-Up Form. The data are stored in the Pfizer safety database (ARGUS) and reported with routine pharmacovigilance activities. Below is a schematic of the TESPO study design (Figure 1).

Figure 1. Study Population Flow Diagram

- Women exposed to tafamidis meghumine/tafamidis during pregnancy or who became pregnant within 1 month after discontinuation of drug
- During the data collection period of April 2020 June 2030
- No exclusions

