## 8.2.1. Inclusion Criteria

Patients must meet all of the following inclusion criteria to be eligible for inclusion in the study:

All women diagnosed with ATTR exposed to tafamidis during or within 1 month prior to pregnancy, reported as exposure during pregnancy (EDP) events in interventional or non-interventional clinical studies in the tafamidis development program, via spontaneous reports, solicited cases or compassionate use reports, will be included in study B3461091.

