## 8.3. Variables

Variables to be evaluated in this study include patient medical/obstetrical history and pregnancy status and outcomes, neonate and infant development status at birth, and at 6 and 12 months of age.

Variable	Description	Data Source
Maternal status		
Obstetrical History Number of pregnancies Outcome of previous pregnancies	Number of pregnancies including current pregnancy Outcomes of previous pregnancies (full term/premature live birth, stillbirth, etc) Number of living children, children born with congenital anomalies History of infertility	EDP form
Date of first day of last menstrual period	DD-MMM-YYYY	EDP form
Estimated date of conception	DD-MMM-YYYY	EDP form
Tafamidis Exposure	Formulation and dosage. Start and stop dates of tafamidis	EDP form
Exposure to concomitant medications that have risk of congenital abnormalities	Dose and start and stop dates of these concomitant medications	EDP form
Gestational age at exposure	Gestational age of fetus at exposure to tafamidis or other medication (weeks or trimester)	EDP form

PFIZER CONFIDENTIAL

CT24-WI-GL02-RF02 1.0 Non-Interventional Study Protocol Template For Secondary Data Collection Study 15-Aug-2018 Page 19 of 42

Variable	Description	Data Source
Medical History Risk Factors	Risk factors for adverse pregnancy outcomes (ie, environmental exposures, eg, hypertension, diabetes, etc.	EDP form
	Family history of congenital abnormality/genetic diseases	
Smoking	Type and number per day	EDP form
Alcohol use	Type and frequency	EDP form
Illicit drug use	Type and frequency	EDP form
Current Pregnancy		,
Maternal assessment at time of study enrollment	Vital Signs BP, temp, pulse	
Smoking during pregnancy	Type and number per day	EDP form
Alcohol use during pregnancy	Type and frequency	EDP form
Illicit drug use during pregnancy	Type and frequency	EDP form
Other relevant medical conditions, use of concomitant medications, other exposures to drugs	Comorbities/hospitalizations during pregnancy/other concomitant medications or treatments taken during pregnancy	EDP form
Maternal assessment during 2 nd trimester	Vital Signs BP, temp, pulse	EDP form

Variable	Variable Description			
Smoking during pregnancy	Type and number per day	EDP form		
Alcohol use during pregnancy	Type and frequency	EDP form		

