## 8.7. Data Analysis

Given the expected low number of reported pregnancy exposures, no formal data analysis or hypothesis testing will be conducted. Data collected on exposures and outcomes will be summarized descriptively. Summaries of the numbers of pregnancies and incidence proportion (percent) of adverse pregnancy and birth events reported via TESPO and/or captured in the standard EDP or SAE form entered into ARGUS will be provided. Women with ATTR exposed during pregnancy to concomitant medications with a known increased risk for congenital anomalies will be excluded from the descriptive summary but will be included in the study and described separately.

There are no known epidemiologic data on the incidence of adverse pregnancy outcomes in the ATTR population. Therefore, epidemiologic data on the incidence of adverse pregnancy outcomes in other populations (eg, the general population, particularly in those regions where tafamidis is commercially available and tafamidis unexposed pregnancies reported in THAOS) may be used to contextualize the findings.

A separate descriptive summary based on prospective and retrospective cases will be performed and submitted to the Agency. Prospective cases are defined as women who enroll prior to the occurrence of the pregnancy outcome (live birth, miscarriage, stillbirth, pregnancy termination). Retrospective cases are defined as women who enroll or contact the registry after the pregnancy outcome has occurred (live birth, miscarriage, stillbirth, pregnancy termination). Stratified analysis of the reported pregnancy outcomes, including pregnancies in women reported prior to start of this protocol, will be performed by daily maternal dose.

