5.2	Does the protocol address the validity of the exposure measurement? (eg, precision, accuracy, use of validation sub-study).				
5.3	Is exposure categorised according to time windows?		$\boxtimes$		
5.4	Is intensity of exposure addressed? (eg, dose, duration).		$\square$		
5.5	Is exposure categorised based on biological mechanism of action and taking into account the pharmacokinetics and pharmacodynamics of the drug?				
5.6	Is (are) (an) appropriate comparator(s) identified?		$\square$		

Comments:

Section	on 6: Outcome definition and measurement	Yes	No	N/A	Section Number
6.1	Does the protocol specify the primary and secondary (if applicable) outcome(s) to be investigated?				8
6.2	Does the protocol describe how the outcomes are defined and measured?				8.7
6.3	Does the protocol address the validity of outcome measurement? (eg, precision, accuracy, sensitivity, specificity, positive predictive value, use of validation sub-study).				

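### Section 8.7 stratifies pregnancy outcomes by daily dose but not by when tafamidis was taken, so the malformation proportion pools pre-conception, first-trimester and later-only exposure and can be pulled toward background

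*Protocol*

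**What the plan says.** Protocol Section 8.2.1 admits "All women diagnosed with ATTR exposed to tafamidis during or within 1 month prior to pregnancy". Section 8.1 describes the same group as including women "who became pregnant within 1 month after discontinuation of drug". Both objectives in Section 7 treat these women as one exposed group and describe malformations as a frequency among the reported pregnancies.

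For the analysis, Section 8.7 states: "Stratified analysis of the reported pregnancy outcomes, including pregnancies in women reported prior to start of this protocol, will be performed by daily maternal dose". It plans two other splits. One is by when the case was reported: "A separate descriptive summary based on prospective and retrospective cases will be performed and submitted to the Agency". The other takes women on co-medication with a known malformation risk out of the main summary and describes them separately. Neither concerns when tafamidis was taken.

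Section 8.3 does collect timing: date of last menstrual period (LMP), estimated conception date, tafamidis start and stop dates, and "Gestational age of fetus at exposure to tafamidis or other medication (weeks or trimester").

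**The concern.** Malformation risk depends on drug being present in a particular part of gestation, and the protocol's own evidence points that way. Section 6.2.2 reports that "oral administration of tafamidis meglumine to pregnant rabbits during organogenesis resulted in adverse effects on development", fetal malformation among them. A pregnancy with practically no drug in that period says little about this hazard, yet it counts fully in the denominator. The same applies to a pregnancy exposed only after that period.

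If such pregnancies carry background risk, pooling moves the reported proportion toward background. For a safety surveillance study that is the unfavourable direction. Section 8.7 also says that findings may be set beside general-population data and unexposed pregnancies in the disease registry, so the dilution would carry into that comparison.

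**Working it through.** The protocol has no sample size, power or risk estimate to reproduce. Two things can be checked: how much drug remains at conception, and what pooling does to a proportion.

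**Inputs from the protocol**
- Half-life (Section 6.2.1): "Tafamidis has an approximate 55-hour half-life".
- Eligible window (Section 8.2.1): during pregnancy, or up to 1 month before.
- Maternal exposures to 25 September 2019 (Section 6): 13, with no split by timing.

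**Assumptions, not in the protocol**
- Simple first-order decline after the last dose.
- The share *s* of pregnancies without relevant exposure.
- The true risk ratio *R* in relevantly exposed pregnancies.
- Background risk in the remaining pregnancies.

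**1. Residual drug at conception.** Half-lives elapsed = days × 24 / 55; residual fraction = 0.5^(half-lives).

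| Days from last dose to conception | Half-lives | Residual |
|---|---|---|
| 1 | 0.44 | 74% |
| 3 | 1.31 | 40% |
| 7 | 3.05 | 12% |
| 11.5 | 5.0 | 3% |
| 14 | 6.1 | 1.4% |
| 21 | 9.2 | 0.17% |
| 30 | 13.1 | 0.01% |

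The pre-conception group is therefore mixed. Some women carry substantial drug into early gestation and others carry practically none. Each further week after conception multiplies the residual by another 0.12.

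**2. Effect of pooling.** With background risk p0, the pooled risk is (1 − s) × R × p0 + s × p0. Dividing by p0 gives an apparent ratio of 1 + (1 − s)(R − 1), so p0 cancels.
- R = 2: s = 10% gives 1 + 0.9 = 1.9; s = 30% gives 1.7; s = 50% gives 1.5.
- R = 3: s = 10% gives 1 + 0.9 × 2 = 2.8; s = 25% gives 2.5; s = 50% gives 2.0.

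**3. Precision.** With 0 events the exact two-sided 95% upper limit is 1 − 0.025^(1/n): 25% for n = 13, and 41% for an assumed stratum of n = 7. Two events in 13 give 15.4% (95% CI 1.9% to 45.4%); two in 7 give 28.6% (3.7% to 71.0%). Separating the groups addresses the bias and widens the interval.

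**The case against.** **A statistical analysis plan could add this.** Tabulating a collected variable by trimester is ordinary table-shell content, and Section 8.7 promises a descriptive summary of exposure data without saying that dose is the only breakdown. It is true that nothing forbids a timing table. But the protocol does not leave stratification open: it names a factor and omits the one that its nonclinical section makes relevant. The point concerns that stated choice.

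**The window edge is not the whole group.** A reader might infer from the 13 half-lives in a month that women who stopped before conception are all effectively unexposed. The half-life does not support this: 40% remains after 3 days and 12% after 7. The objection stands, and it is why the interval since the last dose should be shown.

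**The size is assumed.** This also stands. No timing split exists for the 13 maternal exposures, and at s = 10% the distortion is slight (2 becomes 1.9). Later-only exposure may be uncommon, since Section 6.2.2 notes that labelling advises against pregnancy on treatment. That is an inference and the protocol gives no figure for it.

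**No risk ratio is planned, and small numbers dominate.** Correct. The ratios only illustrate direction, and Section 8.9 already concedes limited interpretability. A reader might infer that a timing split would make a null result reassuring. With upper limits of 25% to 41% for zero events, it would not.

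**The checklist.** One might cite the Annex 1 item "Is exposure categorised according to time windows", which appears to be answered no, as confirmation. Its layout is too broken to rely on, and the neighbouring item on dose appears answered the same way although Section 8.7 stratifies by dose. No weight is placed on it.

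**Conclusion.** The concern holds in a limited form. As written, Section 8.7 yields a malformation proportion that mixes pregnancies with little or no drug in the sensitive period with first-trimester exposures, and nothing in the stated analysis separates them. The likely direction is toward background, provided that pregnancies without relevant exposure carry background risk.

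The size cannot be determined from the protocol. For a true risk ratio of 2 it ranges from slight (1.9) to material (1.5) over assumed shares of 10% to 50%. The documents do not support calling the pre-conception group unexposed as a whole, or claiming that a known signal would be hidden. What they support is that a timing breakdown is relevant on the protocol's own evidence, and feasible with data it already collects.

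**What to change.** In Section 8.7, keep the dose stratification and add a descriptive tabulation, or a case listing where counts are very small, of outcomes by exposure window:

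1. last dose before conception, showing the interval from last dose to conception;
2. any first-trimester exposure;
3. second- or third-trimester exposure only;
4. timing unknown.

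State one origin, LMP or conception, and use it for both the 1-month window and the trimesters. Otherwise a woman whose last dose fell between the two dates could be placed in either group 1 or group 2. Report major malformations for first-trimester-exposed pregnancies separately, next to the overall figure, with numerators and denominators for each. Dose can be shown within that group if numbers allow.

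**Cost.** No new data collection, and one more table dimension. The unknown category is needed because Section 8.9 expects incomplete data and Section 8.3 allows timing to be recorded only by trimester. The downside is small cells. The table reduces dilution but adds no precision, and it should be presented as description only.

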## 8.8. Quality Control

The data for this program will be collected using the forms provided and submitted to the Pfizer Safety Surveillance and Risk Management Department through the DSU. Review by the DSU will be performed according to their standard SOPs.

## 8.9. Limitations of the Research Methods

This study has three major limitations:

- 1. ATTR is a rare disease therefore there is a small number of patients who are diagnosed with the disease and an even smaller number of female patients who become pregnant following exposure to tafamidis. The mean age of the ATTR-PN and ATTR-CM populations are 45 and 75 years old, respectively. Because a small number of pregnancies reported is anticipated, it may limit the interpretability of the study results.
- 2. it is possible to have some incomplete or missing data as there is reliance on the HCP or the pregnant patient to agree to report pregnancy cases and infant follow up to Pfizer.
- 3. not all pregnancy exposure of women with ATTR are being reported.

Every effort will be made to obtain all data elements for reported cases and to increase the awareness of this surveillance program to elicit reporting.

## 8.10. Other Aspects

Not applicable.

## 9. PROTECTION OF HUMAN SUBJECTS

## 9.1. Patient Information

This study involves data that exist in anonymized structured format and contain no patient personal information. All parties will comply with all applicable laws, including laws regarding the implementation of organizational and technical measures to ensure protection of patient personal data. Such measures will include omitting patient names or other directly identifiable data on any sponsor forms, reports, publications, or in any other disclosures, except where required by applicable laws.

To protect the rights and freedoms of natural persons with regard to the processing of personal data, when study data are compiled for transfer to Pfizer and other authorized parties, subject names will be removed.

## 9.2. Patient Consent

The information used in this study is anonymized (ie, the information per se does not identify any patient and cannot be used to re-identify the patients with the available information) before the study is conducted. Therefore, no study-specific consent form is required for this study. However, women participating in TESPO or in sponsored clinical trials will be asked to provide agreement for a release of information from their obstetric and pediatric healthcare provider(s).

## 9.3. Institutional Review Board (IRB)/Independent Ethics Committee (IEC)

The IRB/EC review or approval is not required for this study.

## 9.4. Ethical Conduct of the Study

The study will be conducted in accordance with global and/or local legal and regulatory requirements, as well as with scientific purpose, value and rigor and follow generally accepted research practices described in Good Pharmacovigilance Practices and Pharmacoepidemiologic Assessment FDA Guidance for Industry March 2005.

## 9.5. Record Retention

To enable evaluations and/or inspections/audits from regulatory authorities or Pfizer, study records must be kept for a minimum of 15 years after completion or discontinuation of the study, or longer if required by applicable local regulations.

# 10. MANAGEMENT AND REPORTING OF ADVERSE EVENTS/ADVERSE REACTIONS

As noted in Section 8.2, events of pregnancy will be reported for women with ATTR receiving tafamidis via interventional and non-interventional clinical trials, via spontaneous reporting, through direct contact from patients and health care professionals using the toll-free numbers provided in the labeling documents, through unsolicited requests for pregnancy safety information (via Pfizer Medical Information Department) or through contact with sales representatives.

Regulatory reporting of adverse events/adverse reactions based on data source will occur per standard practice. Pregnancy events described in this study will have met regulatory reporting requirements as applicable based on their initial source (ie, SAE reporting of clinical trials, SAE/AE reporting of NI studies, compassionate use or spontaneous reporting).

## 11. PLANS FOR DISSEMINATING AND COMMUNICATING STUDY RESULTS

Descriptive data from this pregnancy surveillance study will be included in reports according to country/region specific requirements (eg, in periodic safety update reports [PSURs] in EU) at the frequency required by individual country/region regulatory requirements. Among women with ATTR who received tafamidis, these reports will provide of the numbers of adverse pregnancy events and pregnancies reported to TESPO and/or captured in the Pfizer safety database (ARGUS). Information from the study will be communicated to the scientific and medical community through relevant professional association meetings and/or a journal submission. Annual interim reports and the final study report will be submitted to the FDA according to committed timelines (Interim Report: Annually from April 2021 to April 2030; Final Report: December 2030).

In the event of any prohibition or restriction imposed (eg, clinical hold) by an applicable competent authority in any area of the world, or if the party responsible for collecting data from the participant is aware of any new information which might influence the evaluation of the benefits and risks of a Pfizer product, Pfizer should be informed immediately.

